7.3 Stopping Rules

If the incidence of Grade 3 or higher adverse events convincingly exceeds 50%, a threshold we are comfortable with given the potential benefit of the regimen as well as our experience in managing the side effects in this patient population, we will temporarily halt the study and carefully review the available data at that point in order to suggest a potential modification. If we determine that high rates of adverse events are intrinsically related to protocol and no modification will reasonably decrease this rate to an acceptable threshold (below 50%), then we will terminate the study.

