7.1.1 Definitions

An adverse event is defined as any untoward or unfavorable medical occurrence in a human research study participant, including any abnormal sign (for example, abnormal physical exam, imaging finding or clinically significant laboratory finding), symptom, clinical event, or disease, temporarily associated with the subject's participation in the research, whether or not it is considered related to the subject's participation in the research.

Adverse events encompass clinical, physical and psychological harms. Adverse events occur most commonly in the context of biomedical research, although on occasion, they can occur in the context of social and behavioral research. Adverse events may be expected or unexpected.

Acute Adverse Events

Adverse events occurring in the time period from the signing of the informed consent, through 90 days post treatment will be considered acute adverse events.

Late Adverse Events

Adverse events occurring in the time period from the end of acute monitoring, to 1 year post treatment, will be defined as late adverse events. In addition, the study team will review encounters in a select specialty category relevant to study endpoints. These select specialties include hospitalizations, medical oncology, radiation oncology, and urology records and will be limited in scope based on categorization of events (GU/GI) and also the type of records that will be queried (hospitalizations, medical oncology, and radiation oncology).

Severity

Adverse events will be graded by a numerical score according to the defined NCI Common Terminology Criteria for Adverse Events (NCI CTCAE) Version 5.0. Adverse events not specifically defined in the NCI CTCAE will be scored on the Adverse Event log according to the general guidelines provided by the NCI CTCAE and as outlined below.

- Grade 1: Mild
- Grade 2: Moderate
- Grade 3: Severe or medically significant but not immediately life threatening
- Grade 4: Life threatening consequences
- Grade 5: Death related to the adverse event

Serious Adverse Events

OHRP and the UTSW IRB define serious adverse events as those events, occurring at any dose, which meets any of the following criteria:

- Results in death
- Is life-threatening (places the subject at immediate risk of death from the event as it occurred);
- Results in inpatient hospitalization^{1,2} or prolongation of existing hospitalization
- Results in persistent or significant disability/incapacity

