The phrase "unanticipated problems involving risks to subjects or others" is found, but not defined in the HHS regulations at 45 CFR 46, and the FDA regulations at 21 CFR 56.108(b)(1) and 21 CFR 312.66. For device studies, part 812 uses the term unanticipated adverse device effect, which is defined in 21 CFR 812.3(s). Guidance from the regulatory agencies considers unanticipated problems to include any incident, experience, or outcome that meets ALL three (3) of the following criteria:

- Unexpected in terms of nature, severity or frequency given (a) the research procedures that are described in the protocol-related documents, such as the IRB-approved research protocol and informed consent document; and (b) the characteristics of the subject population being studied;

AND

- Related or possibly related to participation in the research (possibly related means there is a reasonable possibility that the incident, experience, or outcome may have been caused by the procedures involved in the research);
AND
- Suggests that the research places subjects or others at greater risk of harm (including physical, psychological, economic, or social harm) than was previously known or recognized. Note: According to OHRP, if the adverse event is serious, it would always suggest a greater risk of harm.

Follow-up

All adverse events will be followed up according to good medical practices.

7.2 Steps to Determine If a Serious Adverse Event Requires Expedited Reporting to the SCCC DSMC and/or HRPP

Step 1: Identify the type of adverse event using the NCI Common Terminology Criteria for Adverse Events (CTCAE v5).

Step 2: Grade the adverse event using the NCI CTCAE v5.

Step 3: Determine whether the adverse event is related to the protocol therapy.

Attribution categories are as follows:

- Definite – The AE *is clearly related* to the study treatment.
- Probable – The AE *is likely related* to the study treatment.
- Possible – The AE *may be related* to the study treatment.
- Unlikely – The AE *may NOT be related* to the study treatment.
- Unrelated – The AE *is clearly NOT related* to the study treatment.

Note: This includes all events that occur up to the end of the acute adverse events reporting period as defined in section 7.1.1. Any event that occurs more than 30 days after the last dose of and is attributed (possibly, probably, or definitely) to the agent(s) must also be reported as indicated in the sections below.

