Step 4: Determine the prior experience of the adverse event. Expected events are those that have been previously identified as resulting from administration of the treatment. An adverse event is considered unexpected, for expedited reporting purposes only, when either the type of event or the severity of the event is not listed in:

- the current known adverse events listed in the Agent Information Section of this protocol (if applicable);
- the drug package insert (if applicable);
- the current Investigator's Brochure (if applicable)
- the Study Agent(s)/Therapy(ies) Background and Associated Known Toxicities section of this protocol

7.2.1 Reporting SAEs and UPIRSOs to the Simmons Comprehensive Cancer Center (SCCC) Data Safety Monitoring Committee (DSMC)

SAEs and UPIRSOs at all sites, which occur in research subjects on protocols for which the SCCC is the DSMC of record, require reporting to the DSMC regardless of whether IRB reporting is required. ***All SAEs occurring during the protocol-specified monitoring period and all UPIRSOs should be submitted to the SCCC DSMC within 5 business days of the study team members awareness of the event(s).*** In addition, for participating centers other than UTSW, local IRB guidance should be followed for local reporting of serious adverse events or unanticipated problems.

The UTSW study PI is responsible for ensuring SAEs/UPIRSOs are submitted to the SCCC DSMC Coordinator. This may be facilitated by the IIT project manager, study team, subsite or other designee. Electronic versions of the eIRB Reportable Event report; FDA Form #3500A forms, or other sponsor forms, if applicable; and/or any other supporting documentation available should be submitted to the DSMC.

UT Southwestern and affiliates will submit documentation via the SAE submission portal. All subsites participating in multi-center study may utilize the Serious Adverse Event Template and submit to the IIT Project Manager, or designee. The DSMC Coordinator will route the form to the DSMC Chair who determines if immediate action is required. Follow-up eIRB reports, and all subsequent SAE or UPIRSO documentation that is available are also submitted to the DSMC Chair who determines if further action is required via the same process. (See *Appendix V of the SCCC DSMC Plan for instructions on how to submit SAEs through the portal and for a template Serious Adverse Event Form which may be utilized by subsites on multi-center IIT studies*).

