If the event occurs on a multi-institutional clinical trial coordinated by the UTSW Simmons Comprehensive Cancer Center, the IIT Project Manager or designee ensures that all participating sites are notified of the event and resulting action, according to FDA guidance for expedited reporting. DSMC Chair reviews all SAEs and UPIRSOs upon receipt from the DSMC Coordinator. The DSMC Chair determines whether action is required and either takes action immediately, convenes a special DSMC session (physical or electronic), or defers the action until a regularly scheduled DSMC meeting.

Telephone reports to Urology CRO, [contact]
Written reports to:
UTSW SCCC Data Safety Monitoring Committee Coordinator Email: [contact] [contact] or deliver to BLB.306
UTSW Institutional Review Board (IRB) Submit a Reportable Event via eIRB with a copy of the final sponsor report as attached supporting documentation

Reporting Unanticipated Problems Involving Risks to Subjects or Others (UPIRSOs) to the UTSW HRPP

UTSW reportable event guidance applies to all research conducted by or on behalf of UT Southwestern, its affiliates, and investigators, sites, or institutions relying on the UT Southwestern IRB. Additional reporting requirements apply for research relying on a non-UT Southwestern IRB.

According to UTSW HRPP/IRB policy, UPIRSOs are incidents, experiences, outcomes, etc. that meet **ALL three (3)** of the following criteria:

1. Unexpected in nature, frequency, or severity (i.e., generally not expected in a subject's underlying condition or not expected as a risk of the study; therefore, not included in the investigator's brochure, protocol, or informed consent document), AND
2. Probably or definitely related to participation in the research, AND
3. Suggests that the research places subjects or others at a greater risk of harm (including physical, psychological, economic, or social harm) than was previously known or recognized. Note: According to OHRP, if the adverse event is serious, it would always suggest a greater risk of harm.

For purposes of this policy, UPIRSOs include unanticipated adverse device effects (UADEs) and death or serious injury related to a humanitarian use device (HUD).

UPIRSOs must be promptly reported to the UTSW HRPP within 5 working days of PI awareness.

Events NOT meeting UPIRSO criteria:

Events that do NOT meet UPIRSO criteria should be tracked, evaluated, summarized, and submitted to the UTSW HRPP/IRB at continuing review.

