9.0 STATISTICAL CONSIDERATIONS

9.1 Study Design/Study Endpoints

This is a single institution, single arm, phase II trial. We hypothesize that the combination of standard-of-care ICI with PULSAR will be feasible and does not result in delays in treatment. We define a target rate of protocol completion (completion of radical cystectomy within sixteen weeks of initiation of PULSAR) of 90%, with a lower boundary of futility at 60%.

The secondary endpoint is efficacy, defined by 2-year recurrence-free survival.

As discussed above, we additionally plan to assess safety (defined by the 90-day rate of Clavien-Dindo Grade \geq III complications following radical cystectomy); pathologic outcomes; rates of residual disease at surgery; and ureteroenteric anastomotic stricture rate.

If the incidence of Grade 3 or higher treatment-related adverse events convincingly exceeds 50%, a threshold we are comfortable with given the potential benefit of the regimen as well as our experience in managing the side effects in this patient population, we will temporarily halt the study and carefully review the available data at that point in order to suggest a potential modification. If we determine that high rates of adverse events are intrinsically related to protocol and no modification will reasonably decrease this rate to an acceptable threshold (below 50%), then we will terminate the study.

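### A treatment-related death does not by itself pause enrolment, because the only study-level halting rule counts Grades 3 to 5 alike against 50%

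*Combined protocol and SAP*

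**What the plan says.** Section 7.3 of the combined protocol and SAP opens its halting rule with "If the incidence of Grade 3 or higher adverse events convincingly exceeds 50%, a threshold we are comfortable with", and justifies the threshold as acceptable "given the potential benefit of the regimen as well as our experience in managing the side effects in this patient population". When the rule is met, the study is temporarily halted and the data reviewed. Section 9.1 repeats it with a causality restriction: "If the incidence of Grade 3 or higher treatment-related adverse events convincingly exceeds 50" per cent. Neither section gives a separate limit for Grade 4 or Grade 5. Section 7.1.1 (Severity) includes "Grade 5: Death related to the adverse event", so deaths fall inside the pooled count.

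Other sections deal with single events. Section 7.2, Step 3, requires the team to "Determine whether the adverse event is related to the protocol therapy" on a five-level scale. Under 7.2.1, serious adverse events in the monitoring period "should be submitted to the SCCC DSMC within 5 business days" of the team learning of them. The form is routed to the Chair, who determines whether immediate action is required, and 7.2.1 adds: "DSMC Chair reviews all SAEs and UPIRSOs upon receipt from the DSMC Coordinator". The Chair then acts at once, convenes a special session, "or defers the action until a regularly scheduled DSMC meeting". Section 10.4 says that the DSMC meets quarterly and reviews serious events in real time. Sections 4.10 and 5.5 cover stopping or removal of individual subjects, not enrolment.

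**The concern.** The reasons given for the 50% limit, potential benefit and experience in managing side effects, suit toxicity that can be managed. They do not suit death. Yet a death adds one to the same numerator as a Grade 3 event that resolves, so the rule can remain unmet after one or more related deaths if other toxicity is moderate.

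This matters because the authors state in section 1.2 that, to their knowledge, neoadjuvant PULSAR for bladder cancer has not been studied. Patients receive checkpoint inhibition and 30 to 36 Gy in three fractions, followed by radical cystectomy. At stake is whether the next patient can be enrolled before someone has looked at a related death and recorded why it is acceptable to go on.

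**Working it through.** **Inputs from the documents.** Limit: above 50% of patients with a Grade 3 or higher event (7.3, 9.1). Enrolment: 27 patients over three years (9.2). DSMC meetings: quarterly (10.4). Related-death rate in the mixed-tumour SAbR trial cited in 1.2: 4.5%, used only as an illustration. The plan gives no operating characteristics for the halting rule, so there is no stated figure to reproduce; the accrual figure does reproduce, 27/3 = 9 per year.

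**Assumptions.** Grade 3-4 rates of 20%, 30%, 40% or 50% in patients who do not die; independent patients; outcomes known before the next enrolment. The word *convincingly* has no definition in the plan; where needed it is read as a one-sided exact binomial p of at most 0.10 against 50%.

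**1. What deaths contribute to the rule.** One death in 27 is 1/27 = 3.7%; two are 7.4%. The point estimate first passes 50% at 14 of 27 (51.9%), so 13 of 27 (48.1%) may have Grade 3-5 events, deaths included, without triggering it. Under the assumed reading of *convincingly*, 18 of 27 are needed.

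**2. Enrolment during a deferral.** 9/4 = 2.25 patients per quarter. This is the most that accrues at the expected rate between a death and the next scheduled meeting. A death at a random time in the quarter waits half as long on average: 2.25/2 = 1.125.

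**3. How well the 50% rule detects deaths (illustration).** Take three related deaths in the first 10 patients. Exceeding 50% needs 6 of 10, hence at least 3 Grade 3-4 events among the other 7: P(X ≥ 3), X ~ Binomial(7, p).

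Then place three related deaths at random among 27 patients and check after each patient up to the 26th, the last look that can still stop an enrolment (400,000 simulated trials). Probability that the rule is met:

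| Assumed Grade 3-4 rate in the others | 20% | 30% | 40% | 50% |
|---|---|---|---|---|
| First 10 patients, above 50% | 15% | 35% | 58% | 77% |
| Checks from 10th patient, above 50% | 7% | 27% | 59% | 85% |
| Checks from 5th patient, above 50% | 19% | 42% | 69% | 89% |
| From 10th, p ≤ 0.10 | 0.1% | 2% | 10% | 32% |
| From 5th, p ≤ 0.10 | 0.5% | 3% | 12% | 35% |

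The result is driven by the other patients' toxicity, not by the deaths.

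**4. How likely that scenario is.** Three or more related deaths in 27, exact binomial: 12% at a 4.5% death rate and 0.2% at 1%. In the first 10 patients: 0.9% at 4.5% and 0.01% at 1%.

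**5. How often a death trigger would act.** Expected related deaths are 27p and the chance of at least one is 1 − (1 − p)^27. For p = 1%, 4.5% and 10% (the first and last assumed), these are 0.27, 1.2 and 2.7 deaths, and 24%, 71% and 94%.

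**6. Cost of a pause.** 9/52 = 0.17 patient per week; two weeks, 0.35; thirteen weeks, 2.25.

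**The case against.** The strongest answer is that the protocol already requires an individual look at every death. The event goes to the DSMC within 5 business days and the Chair must decide whether immediate action is needed. An unexpected, related death is also an unanticipated problem: 7.1.2 counts events that are only possibly related, and all such problems go to the DSMC. The HRPP reporting text is narrower (probably or definitely related) but adds a second route within 5 working days. This stands. The proposed sentence uses the same Chair, so it refines an existing safeguard and does not supply a missing one. What none of these duties does is hold enrolment meanwhile, and deferral is expressly allowed.

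A reader might infer from the table that enrolment would continue after three deaths in the share of trials where the rule is not met. The documents do not support that. Continuation also requires the Chair to take no action after each death, and nothing in the plan says how likely that is. Three related deaths is itself an uncommon scenario at the lower rates. Nor would data be immediate: cystectomy may come up to sixteen weeks after PULSAR starts, and a further 90 days makes about 29 weeks, or roughly five enrolments at nine per year.

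The choice of 50% is a design choice for which the authors give reasons, and the pelvic-node series in 1.2 report minimal toxicity. Both are fair, and neither argues against a separate provision for deaths.

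**Conclusion.** The point holds in a limited form. On the protocol text, no related death by itself obliges an enrolment pause; a pause depends on the Chair's discretion or on the pooled 50% rule, which is a poor detector of deaths when other toxicity is moderate. If the Chair defers, the exposure is about 1.1 further enrolments on average and 2.25 at most, assuming even accrual at the planned rate and quarterly meetings.

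It would go too far to conclude that deaths escape independent review, or that the trial has no means of stopping after one. The institutional DSMC plan and HRPP policy are referenced but were not supplied, and either may contain a hold. The point does not rest on the difference between the all-cause wording of 7.3 and the treatment-related wording of 9.1, which is a separate matter. This is a cheap improvement to patient protection, not an error in the design.

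**What to change.** Keep the 50% rule and add to both 7.3 and 9.1:

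> Any Grade 5 event from the first PULSAR fraction through 90 days after radical cystectomy (or 90 days after the last fraction if no cystectomy is done) judged possibly, probably or definitely related to PULSAR, or to its combination with ICI and cystectomy, pauses new enrolment until the DSMC Chair or a special DSMC session under 7.2.1 has reviewed the case and recorded a written decision to resume, modify or stop; this decision is made on receipt or at a special session and is not deferred to a scheduled meeting.

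The window is stated because 4.10 ends trial therapy at the third fraction while 4.11 follows adverse outcomes to 90 days after cystectomy. Deaths rated unlikely or unrelated do not trigger the pause, and nothing forces termination.

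The change is wording only and uses the existing Chair, attribution scale and reporting timeline. Its cost is short pauses, some for peri-operative deaths judged possibly related, at about 0.17 patient per week. The bar on deferral keeps them short: if deferral were allowed with the pause left in place, one pause could last up to 13 weeks, or about 2.25 patients.

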8.0 CORRELATIVES/SPECIAL STUDIES

Patients have the option to enroll on the UTSW tissue protocol (STU 072010-098) for the collection for sera, PBMC and available tumor tissue to be collected before and during treatment. The protocol consent will include consent for use of tissues in future studies, e.g. molecular profiling.

9.0 STATISTICAL CONSIDERATIONS

9.1 Study Design/Study Endpoints

This is a single institution, single arm, phase II trial. We hypothesize that the combination of standard-of-care ICI with PULSAR will be feasible and does not result in delays in treatment. We define a target rate of protocol completion (completion of radical cystectomy within sixteen weeks of initiation of PULSAR) of 90%, with a lower boundary of futility at 60%.

The secondary endpoint is efficacy, defined by 2-year recurrence-free survival.

As discussed above, we additionally plan to assess safety (defined by the 90-day rate of Clavien-Dindo Grade \geq III complications following radical cystectomy); pathologic outcomes; rates of residual disease at surgery; and ureteroenteric anastomotic stricture rate.

If the incidence of Grade 3 or higher treatment-related adverse events convincingly exceeds 50%, a threshold we are comfortable with given the potential benefit of the regimen as well as our experience in managing the side effects in this patient population, we will temporarily halt the study and carefully review the available data at that point in order to suggest a potential modification. If we determine that high rates of adverse events are intrinsically related to protocol and no modification will reasonably decrease this rate to an acceptable threshold (below 50%), then we will terminate the study.

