1.0 BACKGROUND AND RATIONALE

1.1 Disease Background

Muscle invasive bladder cancer (MIBC) has high metastatic potential and warrants aggressive treatment. Standard-of-care treatment in MIBC involves platinum-based neoadjuvant chemotherapy (NACT) followed by radical cystectomy (RC) with pelvic lymph node dissection (PLND) and urinary diversion¹⁻³. Bladder-conserving chemoradiation therapy is an appropriate alternative in select patients, though it is used in only a minority of cases in the United States⁴. Bladder cancer carries significant morbidity and mortality and has been cited as the most expensive malignancy to manage, on a per-patient basis, in the United States^{5,6}.

Metastatic spread to regional lymph nodes is an adverse prognostic factor in bladder cancer. In several large case series reported without use of neoadjuvant chemotherapy, patients with pathologically positive lymph nodes (pN+) at radical cystectomy had 5-year overall or disease-specific survival rates of only 22-30%⁷⁻¹⁰. The addition of neoadjuvant chemotherapy (NACT) or downstaging chemotherapy (DCT) in patients with clinically positive lymph nodes (cN+) improves outcomes, particularly in those who achieve a pathologic complete response to DCT^{11,12}. However, patients who fail to respond to downstaging or neoadjuvant chemotherapy have an especially poor prognosis, with a 5-year overall survival rate of only 16% in one recent series¹³. It should also be noted that a significant proportion (up to 25-50%) of patients with bladder cancer are ineligible for chemotherapy due to medical comorbidities¹⁴.

We recently reviewed the outcomes of patients undergoing radical cystectomy at UT Southwestern with bulky cN+ bladder cancer¹⁵. Among the subset of patients who did not receive or failed to respond to DCT, the 2-year progression-free survival was only 30%, despite aggressive salvage treatment. Importantly, a majority of patients (84%) in the study received downstaging chemotherapy and all were medically eligible for chemotherapy. This suggests that chemo-ineligible patients presenting with cN+ disease were not offered curative treatment. Direct comparisons with historic literature are difficult, due to widely varying definitions of cN+ disease; however, the progression-free survival of our bulky cN+ cohort closely parallels that of the cN2-3 and cM1a cohorts within one large published series¹¹, confirming that our bulky cN+ cohort represents an especially high-risk population.

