2.2 Secondary Objectives

2.2.1 To determine the 2-year progression-free survival (PFS) in patients with cN+ bladder cancer in all enrolled patients, and in the subset of patients completing the full protocol of ICI + PULSAR + RC.

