9.2 Sample Size and Accrual

For the primary endpoint of feasibility, we define a target rate of protocol completion (completion of radical cystectomy within sixteen weeks of initiation of PULSAR) of 90%, with a lower boundary of futility at 60%. A sample size of 24 patients provides 91% power to reject a 60% completion rate at a two-sided alpha of 0.05. Of note, this sample size was employed in the recent NABUCCO trial, which addressed a similar high-risk patient cohort³⁶. Allowing a 10% drop out rate increases the desired enrollment to a total of **27 patients**. Given the desired enrollment of 27 patients and the three-year trial period, this will require accrual of nine patients per year across all sites.

For the secondary endpoint of progression-free survival, the trial-eligible subset of our recently published historic series of cN+ bladder cancer patients achieved a 2-year recurrence-free survival rate of 30%¹⁵. A sample size of 24 patients provides 90% power to detect a 27% absolute increase in 2-year recurrence free survival with a one-sided alpha of 0.10 using the Kaplan-Meier log-rank test.

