9.3 Data Analyses

The primary endpoint, protocol completion, will be assessed by calculating the proportion of patients completing radical cystectomy within sixteen weeks of initiating PULSAR treatment. If the proportion of patients undergoing cystectomy exceeds 60%, the null hypothesis (that use of ICI+PULSAR+RC is not feasible) will be deemed to have been rejected.

For the secondary endpoint, progression-free survival will be determined as described above, and will be reported by means of Kaplan-Meier survival curves, median progression-free survival time, and proportion of patients without progression at two years. Comparison will be made to the trial-eligible subset of patients in a historic control series using the log-rank test. The 2-year progression-free survival rate in the historic cohort was 30%. The null hypothesis will be rejected if the one-sided *p* value for the comparison is less than 0.10.

Additional planned analyses include the following, all of which will be reported with simple descriptive statistics (*n* / *N* and percentage):

Major complication rate: A major surgical complication will be defined as any postoperative complication of Clavien-Dindo Grade III or higher.

Pathologic outcomes: Pathologic outcomes will be defined as follows, based on the final surgical pathology report:

1. Pathologic complete response: no viable disease remaining in the specimen (ypT0 N0).
2. Pathologic non-muscle-invasive downstaging: primary tumor without muscle invasion, and no viable disease in lymph nodes (\leq ypT1 N0).
3. Pathologic organ-confined downstaging: primary tumor confined to detrusor muscle, and no viable disease in lymph nodes (\leq ypT2 N0).
4. Nodal complete response: no viable disease in lymph nodes, regardless of primary tumor stage (ypTany N0).

Residual disease: Residual disease at surgery will be defined as follows:

1. Microscopic residual disease (R1) will be defined as any positive soft tissue margin on the final surgical pathology report, excluding carcinoma *in situ* at ureteral margins.
2. Gross residual disease (R2) will be defined as any grossly positive tissue margin reported on a pathology report, *or* the operating surgeon's subjective report of grossly unresectable disease including bulky matted lymph nodes.

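### Sections 9.1 and 9.2 call the efficacy endpoint and its 30% benchmark recurrence-free survival, the rest of the plan calls them progression-free survival, and the benchmark is not shown to match the trial's PFS definition

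*Combined protocol and SAP*

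**What the plan says.** Section 9.1 defines the endpoint: "The secondary endpoint is efficacy, defined by 2-year recurrence-free survival".

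Section 9.2 uses both names in one paragraph. It begins "For the secondary endpoint of progression-free survival, the trial-eligible subset of our recently published historic series" and goes on, in the same sentence, to say that this subset "achieved a 2-year recurrence-free survival rate of 30" per cent. The power statement follows: "A sample size of 24 patients provides 90% power to detect a 27% absolute increase in 2-year recurrence free survival", at a one-sided alpha of 0.10 with a log-rank test.

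Section 9.3 analyses PFS, compares it with the historic subset by log-rank test at one-sided p < 0.10, and gives the benchmark as PFS: "The 2-year progression-free survival rate in the historic cohort was 30" per cent. Section 1.1, citing the same reference 15 as 9.2, also calls it PFS: "the 2-year progression-free survival was only 30%, despite aggressive salvage treatment".

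The objective in 2.2.1 is "To determine the 2-year progression-free survival (PFS) in patients with cN+ bladder cancer in all enrolled patients", and also in those who complete the full protocol. Sections 2.4.1 and 6.1.6 give PFS a list of events and start the clock at the first PULSAR treatment. The Study Summary names PFS as the secondary endpoint. RFS is spelled out in the List of Abbreviations and defined nowhere.

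**The concern.** This is the plan's only efficacy comparison with a power statement and a decision rule; the other efficacy and surgical outcomes in 9.3 are descriptive. Its endpoint has two names, and so does the number that it is judged against.

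The names need not mean the same thing here. Recurrence ordinarily presupposes that disease has been removed. Section 2.3.1 expects some patients to progress to unresectable disease before surgery, and 2.4.1 and 6.1.6 provide for gross residual disease. The PFS event lists cover such patients. An undefined RFS does not say how they count.

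The practical stake is the comparator. A log-rank test against historic patients is fair only if both groups are timed from a similar point and counted on the same events. If the historic times run on another definition, both the 30% and the test are affected.

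**Working it through.** **1. Reproduce the stated power.** Inputs from 9.2: n = 24, historic rate 0.30, target 0.30 + 0.27 = 0.57, one-sided alpha 0.10.

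- Exact binomial, success if at least 11 of 24 are event-free at two years. Alpha = P(X ≥ 11 | 24, 0.30) = 0.074; power = P(X ≥ 11 | 24, 0.57) = 0.904. A cut of 10 gives alpha 0.153, so 11 is the smallest cut that keeps 0.10.
- One-sample log-rank, exponential survival: hazard ratio = ln 0.57 / ln 0.30 = 0.467; events expected under the target = 24 × (1 − 0.57) = 10.3. Power runs from 0.88 to 0.96 depending on the variance used; simulation gives 0.927.

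The stated 90% is reproduced. The calculation uses only two rates and a sample size, so renaming the endpoint changes no figure if 30% is the right rate for the endpoint analysed.

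**2. Compare the trial endpoint with the benchmark.**

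| | Trial PFS | Historic 30% |
|---|---|---|
| Name | PFS (RFS in 9.1 and parts of 9.2) | PFS in 1.1 and 9.3; RFS in 9.2 |
| Population | All enrolled, plus completers (2.2.1) | Subset of patients undergoing radical cystectomy (1.1, reference 15) |
| Events | Listed in 2.4.1 and 6.1.6 | Not stated |
| Start | First PULSAR treatment | Not stated |

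**3. How far apart the start dates could be.** Section 4.1 has three fractions at 12 to 16 day intervals, then cystectomy 4 to 8 weeks later. First fraction to surgery is 2 × 12 + 28 = 52 days to 2 × 16 + 56 = 88 days, or about 7 to 13 weeks. If the historic clock starts at surgery (an assumption), the trial clock starts that much earlier for a patient treated on schedule. The direction of any bias is not fixed: trial patients can fail before surgery, which lowers their rate, but their two-year window ends sooner after surgery, which raises it.

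**4. What a different benchmark would do.** The documents give one historic figure, so the range here is assumed. Hold the target at 0.57 and use power = Φ{[(0.57 − S0)√24 − 1.2816√(S0(1 − S0))] / √(0.57 × 0.43)}:

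| Comparable benchmark S0 | Power |
|---|---|
| 0.25 | 0.98 |
| 0.30 | 0.93 |
| 0.35 | 0.83 |
| 0.40 | 0.66 |

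The 0.30 row is this approximation's counterpart to the exact 0.904. In a simulated one-sample log-rank test against a fixed 30%, the false-positive rate is 0.087 when 30% is true, 0.21 when the true null rate is 35%, and 0.39 when it is 40%. These results show sensitivity only. Nothing in the documents says that the benchmark is off by these amounts.

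**The case against.** The strongest reply is that this is loose wording. One sentence of 9.2 uses both names for one quantity from one reference. PFS appears in every other operative place and alone has events and a start date. The event list itself speaks of recurrent disease, and the follow-up schedule in 5.4 records recurrence status. Section 9.3 fixes PFS, the test and the threshold. All of this stands: one endpoint was very probably meant, and RFS has no events, start date or population that an analyst could switch to.

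A reader might go further than the documents allow in three ways.

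- *That one figure cannot be both an RFS and a PFS rate.* In a series where every patient had cystectomy, the two rates may be close or equal.
- *That 9.1 excludes the patients with the worst outcome.* It states no exclusion, and 2.2.1 names all enrolled patients.
- *That PFS can be converted to RFS by dividing by the 60% or 90% completion rates, and a false-positive rate read off.* Those are the trial's futility and target rates for protocol completion, not resection rates in the historic series. In a cystectomy series the resected fraction is 1, and the conversion gives no gap.

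The reply does not settle comparability. Agreeing on the name PFS does not show that the 30% was counted on the trial's events or from a pre-surgical start.

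**Conclusion.** The contradiction is in the operative text and should be corrected before analysis. It is a fault of naming and definition, not a demonstrated power error: the 90% reproduces (0.904, exact binomial) and does not depend on the label.

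The substantive residue is that the documents do not show the historic 30% to be on the definition used for the trial's PFS. Any effect on the log-rank comparison cannot be sized without the series' event definition and start date; the assumed 25% to 40% range shows only that the design is sensitive to this number. The primary feasibility endpoint is not affected.

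**What to change.** - In 9.1 and 9.2, replace recurrence-free survival with progression-free survival and refer to the definition in 2.4.1 and 6.1.6. Their wording is not identical, so settle on one list and cite it.
- Tabulate the in-house historic subset used in the log-rank test with that event list and a comparable pre-cystectomy start date where the records allow. Where they do not, state the start date used.
- Confirm or correct the 30%, and restate the 9.2 power sentence with the resulting figure and its definition.

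The cost is a few words in two sections and a small re-tabulation of the institution's own data. The benchmark or the power may come out slightly less favourable.
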